1.3 ATB Dose and Schedule

ATB has been administered in clinical studies for upper aerodigestive disease prevention in wide ranges of agent doses and schedules, summarized in Table 2 below. Tablet strength in all of these studies was 300 mg. The dose range used in clinical trials was from 2,400 mg/d to 4,800 mg/d. The duration of therapy ranged from two months to five years.

In the current trial, the dose of ATB is in the mid-range (3,600 mg/d), but significantly shorter duration, compared to other ATB studies.

| Study description | Dose/schedule |
|---|---|
| SATCM (State Administration of Traditional Chinese Medicine) Multicenter Trial, 380 hospitals, 24,275 pts | 8 tabs BID (4,800 mg/d) x2 months ON, 1 week OFF= one cycle Duration 2 years |
| Oral Leukoplakia n=150 ATB; control =148 | 8 tabs BID (4,800 mg/d) x 2 months |
| Oral Leukoplakia. n=59 ATB; n=53 placebo (8) | 4 tabs TID (3,600 mg/d) |
| Henan province 1983 Esoph dysplasia, ZSP N=744 agent; n=777 placebo | 8 tabs QD (2,400 mg/d) x 5 years |
| 1984 Hebei Province N=300 randomized to ZSP and n=149 control | 8 tabs BID (4,800/d) x 6 months |
| Table 2: Summary of clinical trials illustrating dose and schedule of ATB. | |

1.4 ATB Safety and Toxicity

Toxicology studies performed in China, translated and summarized in the enclosed ATB Health Canada Application Supporting Documentation, indicates very low acute toxicity and no obvious pathologic changes in organs from chronic toxicology testing, as well as no mutagenic effects from the Ames test. Previous studies of ATB, described in the ATB Health Canada Application Supporting Documentation, have been performed in China for prevention of upper aerodigestive

| Item | Before Treatment | After 3 month | P |
|-------------------------------|------------------|---------------|-------|
| White Blood Cells (10^9) | 6.14+2.22 | 5.62+1.59 | <0.05 |
| Red Blood Cells (10^{12}) | 4.73+0.84 | 4.57+0.43 | >0.05 |
| Hemoglobin (g/l) | 121.12 +21.88 | 121.74+16.63 | >0.05 |
| Platelets (10^9) | 170.65+8.33 | 159.43+7.09 | <0.05 |

Table 3. Effect of ATB (ACAPHA) on blood parameters following chemoradiation

cancer prevention. These studies were placebo controlled and utilized long durations of therapy from two months to five years. In China, there is a general acceptance and common use of natural compounds to treat and prevent disease. The style of reporting of clinical trials of natural compounds reflects this difference compared to the West. Toxicity is qualitatively described in these trials as having low rates of adverse events and high compliance rates even for durations of administration lasting years. In the Hebei Province study of 300 participants randomized to ATB (ZSP) for a duration of six months (taking eight tablets BID (4,800 mg/d)), no toxicity was observed, including no side effects related to blood, liver, or kidney function.

In the largest trial (24,275 patients), the SATCM study, blood parameters were reported on a subgroup of 349 patients from the SATCM study, who received ATB for three months following completion of definitive chemoradiation for cancer treatment. Minor or non-significant changes were observed in blood parameters. The authors of the SATCM study concluded that, overall, ATB had little associated chronic toxicity ("some" patients with loose stool, and a "few" with jaundice and rash). They conclude further that ATB was safe for long-term administration. The SATCM study included patient-reported questionnaires that surveyed a large array of upper intestinal symptoms associated with esophagitis and GERD pre- and during therapy. The study showed improvement of symptoms in the ATB group compared to control. Although previous clinical trials did not specifically examine the effects of ATB on surgical risk, past studies had included biopsies without report of bleeding or healing complications. As a safeguard, however, we have included in our amended protocol, a preoperative coagulation test.

A PK run-in study of ATB in oral cancer patients is currently active at MCW. This trial has examined safety and tolerability of ATB in four patients and two additional patients may be needed to finish this trial. A companion trial in eight normal subjects at University of Houston using the same dose has provided PK information and examined safety/tolerability of ATB as well. Taken together, there were no safety or tolerability concerns remaining to be addressed before randomized trial of ATB. Therefore, we believe that it is time to initiate randomized trial of ATB.

1.5 Preclinical Studies: Mechanism of Action, Efficacy, ATB Key Active Components

There are six plants in ATB, described above, and the presence of each of the plants can be verified using a standard thin layer chromatography (TLC) method based on the official *Compendium of Chinese Pharmacopeia*. However, the only compound used in the product's current quality control criteria was matrine, which was only moderately active against lung cancer cell line LM1. To identify additional compounds useful for QA and QC purposes, we performed activity guided fractionation of ATB (12), and identified the following three compounds from a more active fraction GS409 using oral cancer cell line SCC2095: fraxinellone, dictamnine and maackiain (see Fig.1 for structures, and Table 2 for activities). Trifolirhizin is also expected to be highly active because it is rapidly biotransformed to maackiain *in vivo* (13).

[figure not shown]

Fig 1. Chemical structures of key active compounds present in ATB and active against lung tumor cell lines LM1 and/or oral cancer cell line SCC2095.

Chemopreventive Efficacy of ATB in 4NQO-Induced Oral Carcinogenesis.

We evaluated the chemopreventive efficacy of ATB on the development of 4-nitroquinoline-1-oxide (4NQO)-induced oral SCC in A/J mice.(13) A progression protocol was used in this study by which administration of ATB was initiated in the diet (at 3:7 ratio in AIN76A powder diet) for eight weeks following the first dose of 4NQO. The ATB-containing food was the sole food supply for mice eight weeks after the first dose of 4NQO and continued for 24 consecutive weeks. The details of the experiment are described in our recent paper. (12) In the paper, we showed that ATB inhibited 4NQO-induced oral cancer development by ~60%. In addition, we did not observe any body weight changes in

ATB-treated mice. To investigate the effects of ATB on cell proliferation, we quantified Ki-67 stained cells in normal, dysplastic, and SCC oral epithelium and found that ATB inhibited Ki-67 in both dysplasias and SCCs.(13) Recently, we have shown ATB exhibited a significant inhibitory effect on benz(a)pyrene [B(a)P]-induced lung tumorigenesis in A/J mice using the human equivalent dose of ATB (4 g/kg which equals to 12 mg/mouse by oral gavage) in the diet ($p < 0.05$; **Fig 2**), which used a lower dose than our published study but was equally as effective.

1.6 ATB Mechanism of Action

ATB Inhibits Oral Cancer Cell Tumorigenesis via Inhibition of NF-κB Signaling Pathway.

As the NF-κB signaling pathway is

known to play a major role in oral cancer tumorigenesis, (14-17) we examined the effects of ATB in NF-κB signaling pathway via NF-κB proteomic array in order to validate the RNA seq result

[figure not shown]
[figure not shown]

Fig 2. Inhibition of B(a)P-induced lung tumorigenesis in A/J mice using human equivalent dose of ATB (4g/kg) in the diet.

(Fig. 4 C, D). As predicted from the RNA seq, ATB inhibited NF- κ B signaling pathway as NF- κ B inhibitory proteins I κ B α and SOCS6 were upregulated while NF- κ B activating proteins (both p50/p105 and p52/p10) and RelA were downregulated in ATB-treated SCC15 oral cancer cells compared to that of vehicle control-treated cells (Fig. 3). Growth of oral cancer cells, SCC9 and SCC15 was also inhibited to ATB treatment in a dose-dependent manner (Fig. 4A).

We also further validated the effects of ATB on NF- κ B signaling in SCC9 oral cancer cells via Western blot (Fig. 4C), which confirmed that ATB treatment downregulated key components of NF- κ B signaling pathways in SCC9 oral cancer cells. The functional role of the NF- κ B signaling pathway in ATB efficacy was further validated with H1299 lung cancer cells expressing dominant negative I κ B α .

Growth rate was significantly inhibited in H1299 cells expressing I κ B α dominant negative compared to that of control and they were resistant to ATB treatment whereas control H1299 cells were sensitive to ATB treatment in terms of cell proliferation (Fig. 4B). It has been reported that expression of dominant negative I κ B α suppressed oral cancer proliferation, survival, and tumor growth both *in vitro* and *in vivo*, (17) which indicate the important role of NF- κ B signaling pathway in oral cancer tumorigenesis. We are performing the same experiments with SCC9 and SCC15 oral cancer cell lines expressing dominant negative I κ B α and a similar result is expected. Therefore, we propose that NF- κ B pathway plays a key role in mediating the efficacy of ATB in oral cancer.

1.7 ATB Key Active Components

The efficacy of ATB is further illustrated in preclinical studies that examined the key components of ATB and that, in particular, examined varying concentrations of the key components. We call the concentrated forms of the three compounds, ATB-KAC α . For comparison purpose, the IC₅₀ values (*in μ g/ml*) were 1963 for ATB, 303 for GS409, and 90 for ATB-KAC α (Fig. 5). Therefore, **ATB-KAC α (target IC₅₀ of 90 μ g/ml) will be at least 21-fold more active than ATB**, and it will contain at least 50% of three most active compounds (i.e., fraxinellone, dictamnine, and maackiain, Fig. 1). The

[figure not shown]

Fig 4. Proposed Mechanism of ATB in the Inhibition of HNSCC Tumorigenesis A) ATB inhibited cell proliferation of both SCC9 and SCC15 in a dose-dependent manner. B) Induction of I κ B α dominant negative in H1299 lung cancer cells abrogated anti-proliferative effects of ATB compared to that of control H1299 cells. C) SCC9 oral cancer cells treated with ATB and NF- κ B pathway were examined by Western blot. ATB inhibited NF- κ B pathway in SCC9 oral cancer cells compared to that of cells treated with vehicle control. D) Proposed mechanism of ATB in the inhibition of HNSCC tumorigenesis based on the preliminary data.

[figure not shown]

Fig 5. IC₅₀ Values of ATB, GS409 and projected IC₅₀ value of ATB-KAC α .

concentrated forms of these three compounds is the subject of ongoing *in vitro* investigation which will lead to future clinical investigation of ATB-KAC α .

ATB-KAC α has a well-defined chemical composition unlike a natural compound which can be affected by environmental factors. This approach of simplifying natural product extract to something that is better defined has been used repeatedly in the past for cancer prevention (15, 16).

1.8 Window of Opportunity Study Design

A window of opportunity (WOO) trial design (17), similar in concept as a phase 0 trial design, is well established and is typically used in the early development of novel targeted anti-cancer agents (17). Employing this trial design, a study participant will receive a novel agent (or placebo, in a double-blinded randomized study) for a short duration during the standard waiting period prior to their definitive anticancer treatment, which is nearly always surgery in the case of oral cancer. Traditional clinical endpoints (such as objective response) are typically not the primary objective in WOO or phase 0 trials.

Most commonly, the primary objective is to determine whether an agent achieves its desired or predicted biologic/molecular effects, and/or PD/PK parameters. The utility of these biomarker-based early phase trials for oral pre-malignancy, such as proposed here, has been highlighted by Szabo. (18) A head and neck cancer clinical trial examined erlotinib in a similarly designed trial with a window duration of 7 to 14 days. (19) This study demonstrated significant reduction of Ki67 as well as alteration of multiple other biologic markers of response following a short window of treatment prior to surgery. This study illustrates the utility of the phase 0 or window of opportunity trial design in which, even with a short duration of treatment, mechanistic questions of biologic tumor targets can be addressed. This study of ATB is part of a larger project in which we ultimately wish to examine the chemo preventive effects of ATB in oral pre-cancer lesions. Examination saliva PK of ATB, as we propose in this study, will establish bioavailability of the agent in direct exposure to oral mucosa.

The clinical trial study design, proposed here, is shown in study schema. This single arm open label WOO trial of ATB will enroll patients with resectable stage I-IVB squamous cell cancer of the oral cavity who are candidates for surgical tumor resection. Participants will agree to allow a portion of the standard of care (diagnostic tumor biopsy) to be used for the study, and to take study agents ~~or placebo~~ for a duration (7 to 28 days) until the time of their surgery. A second, post-treatment tumor biopsy is not needed because the OR-resected tumor will serve this purpose. Pre-and post-treatment CT scans will be performed on patients for correlation of Δ Ki67 with change in tumor size and diffusion-weighted MRI.

2 HYPOTHESIS AND OBJECTIVES

We hypothesize that oral administration of ATB will have desirable PK properties and biomarker responses oral cancer.

This hypothesis will be testing in a single-arm, open-label WOO clinical trial evaluating ATB and comparing control tissue bank specimens from untreated patients by blinded review.

2.1 Primary Objectives

To determine the antiproliferative effects of ATB as determined by tumor Ki-67.

2.2 Secondary Objectives

1. Characterize the pharmacokinetic (PK) and pharmacodynamic (PD) properties.
2. Determine the biologic correlates of response, including NFKB, and RNASeq.

2.3 Primary Endpoint

Determine the antiproliferative effects of ATB as determined by tumor Ki-67 in baseline tumor biopsy compared to resected tumor tissue following treatment and utilizing tissue bank specimens as control.

2.4 Secondary Endpoint

To examine PK and PD properties from the saliva samples collected during the period of the study and biologic correlates of response including NFKB, and RNASeq from the tumor specimens collected at baseline and on the day of surgery.

3 STUDY DESIGN

3.1 General Description

A window of opportunity (WOO) Clinical Trial permits examination of drug effects on cancer patients during the “window” between diagnosis of their cancer and their definitive cancer surgery. Similar to the phase 0 study design, the WOO trial design permits examination of the biologic effects of a drug. This is a single arm, open-label window of opportunity study of ATB.

Upon initiating study treatment, patients will start taking study drug. The duration of treatment will depend upon scheduling of their surgery—typically, from the time surgery is scheduled, it will be between seven to 28 days. Four (300 mg) pills will be taken three times per day until the evening prior to surgery. A pill diary will be completed by the patient.

While taking study medication, patients will be required to provide saliva samples. Patients will be given specimen tubes and will store collected samples in the freezer. Saliva sample tubes will be prelabeled to reflect the time of collection (Dose 1- morning, Dose 2-midday and Dose 3- evening). The patients’ diaries will contain checkbox reminders for daily saliva collection. Approximate 1 ml of saliva will be collected. Participants will store collected saliva in storage container provided by the study coordinator in their home freezer.

At the end of the course of therapy, patients will be asked to return the storage specimens to the study coordinator. Patients will be given a Styrofoam transportation container with freeze packs for this purpose. All the specimens will be collected on the day of their surgery.

Saliva samples (1 ml) will be collected at the following timepoints: day 1: then to the evening of the day prior to surgery: A total of at least two patient samples (saliva) will be collected daily corresponding to agent dose timepoints (Dose 1- morning, Dose 2-midday or Dose 3- evening). Saliva samples will be collected in a 5-ml bio vial, time documented by patient, and then frozen and stored by the patient until collection. Patients will be given supplies for saliva collection, storage, and for transportation at the end of the collection period. Compliance of $\geq 90\%$ saliva sample collection is deemed acceptable. Sample storage will be in an airtight container at 0 to - 20° C until batch shipment to [name] laboratory at the University of Houston. The blood, saliva, and tumor tissue specimen should be shipped in dry ice to the following location:

[name]
Department of Pharmacological and Pharmaceutical Sciences
College of Pharmacy
[name]
University of Houston
Houston, TX 77204
Contact Information: [contact]

Participants will continue taking ATB for a total of seven to 28 days, which they will record in a study diary. ATB administration must not exceed more than 28 days. The study diary will be collected at the completion of the study.

At the end of the course, patients will be asked to return the storage specimens to the study coordinator. Patients will be given a Styrofoam transportation container with freeze packs for this purpose. All the specimens will be collected on the day of their surgery.

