5.6 Biopsy specimen, Operative Specimen, and Tissue Processing

Baseline tumor specimens will be analyzed for Ki67 and ATB accumulation and stored for tissue banking for future research. For ATB accumulation studies, tumor and peritumor samples (>150 mg each per patient) should be snap frozen in liquid N2 and stored at -80C freezer until it is shipped. **The samples for ATB accumulation studies should not be fixed in formalin.** Submission of a block is preferred and is highly encouraged. If a block is not available, please provide at least five unstained slides. The block (or unstained slides) should be hand delivered to the CRI Histology Core (address below): The contact person is [name] ([contact]). Enrollment may proceed prior to receipt of outside biopsy specimen if it can be confirmed that there is sufficient tissue and sample will be released.

A portion of the OR-resected tumor will serve as post treatment specimen for comparison to the pre-treatment biopsy. At the time of surgery, a portion of the resected tumor will be utilized for the study. When possible, separate the tumors from the surrounding peritumor tissue. The specimen (i.e., tumor and peritumor) (minimum of 150 mg each) should be fresh frozen in liquid N2 and then stored in -80C freezer **without** formalin fixing. Any remnant tissue will be stored for further testing of biological correlates as mandated by the protocol.

The resected tumor will be received and processed by the MCW Tissue Bank staff. The tissue will be fixed in 10% buffered formalin as soon as resected, grossed into cassettes and processed into paraffin blocks. Once the blocks are in paraffin, they will be delivered to the CRI Histology Core for Ki67 testing. The paraffin block of the resected tumor and biopsy should be delivered to the following location:

[name]

Wisconsin Diagnostics Laboratories

[name]
Milwaukee, WI 53226

Immune response biomarker assessment (such as multiplex immunofluorescent staining) will be performed on biospecimens. Additional immune response testing will be performed based on initial results.

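### Within each patient, saliva storage age runs exactly opposite to day on ATB, so any progressive analyte loss would look like rising exposure

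*Combined protocol and SAP*

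**What the plan says.** Section 3.1 (General Description) sets out the saliva handling:

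- Frequency: "A total of at least two patient samples (saliva) will be collected daily corresponding to agent dose timepoints", from day 1 to the evening before surgery.
- Place: "Participants will store collected saliva in storage container provided by the study coordinator in their home freezer".
- Record: each tube has its "time documented by patient, and then frozen and stored by the patient until collection".
- Hand-over: "All the specimens will be collected on the day of their surgery", in a Styrofoam container with freeze packs.
- Temperature: "Sample storage will be in an airtight container at 0 to - 20° C until batch shipment to" the assay laboratory. No shipment date is given. The shipment itself is on dry ice.
- Course: "Participants will continue taking ATB for a total of seven to 28 days".

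For tumor and peritumor tissue used in the ATB accumulation studies, Section 5.6 requires snap freezing, with samples then "stored at -80C freezer until it is shipped".

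Saliva PK is part of the secondary endpoint (Section 2.4). Section 1.8 says it will establish bioavailability at the oral mucosa. Section 7.1 plans a time-dependent Emax model and mentions no term for storage time. The only stability figure, 90 days in Section 5.3, is for tablets at room temperature.

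**The concern.** Nothing is collected before surgery, so a patient's earliest samples are always the oldest when handed over. If concentration falls with time in the freezer, early values are lowered more than late ones, and a constant true level shows as an increase over the course. Time on drug is also the axis of the planned PK model. Two patients with different course lengths would have day-1 samples that differ through handling alone.

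The permitted range reaches 0 °C, which does not by itself ensure that a sample is frozen. It also applies until shipment, so it covers the wait after surgery. Enrollment is expected to take about 24 months (Section 3.2), so samples from early patients could wait a long time for a batch.

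What is at stake is how far the saliva concentrations can be trusted, both in level and in their course over time. The primary Ki-67 endpoint and its sample size do not depend on saliva.

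**Working it through.** The documents give no figure for saliva stability, so there is none to reproduce. The storage ages follow from the schedule. The loss rate is an assumption and is shown as a range.

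**1. Storage age at hand-over.** Take D dosing days with surgery on day D+1. A sample from day d has been stored s = D + 1 - d days.

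- D = 7: first sample 7 days, last sample 1 day.
- D = 14: 14 days and 1 day.
- D = 28: 28 days and 1 day.

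**2. Relation to day on ATB.** Within a patient, D is fixed and s falls by one for each extra day, so the correlation of s with d is -1.0. In a linear model, s equals a patient constant (D + 1) minus d, so it is an exact combination of the patient effect and the day. This was checked on 14 patients (the target number treated with ATB) with an illustrative mix of course lengths from 7 to 28 days. The design had 14 patient effects, a day term and a storage term, 16 columns in all, and its rank was 15. A linear storage trend cannot be estimated separately from a linear time-on-drug trend within patients.

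**3. Size if loss occurs.** Assume a flat true concentration and first-order loss of a fraction L per day. Recovery is (1 - L)^s, so the apparent last-day to first-day ratio is (1 - L)^-(D - 1).

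| Assumed loss per day | D = 7 (exponent 6) | D = 14 (exponent 13) | D = 28 (exponent 27) |
|---|---|---|---|
| 0% | 1.000 | 1.000 | 1.000 |
| 0.5% | 1.031 | 1.067 | 1.145 |
| 1% | 1.062 | 1.140 | 1.312 |
| 2% | 1.129 | 1.300 | 1.725 |
| 5% | 1.360 | 1.948 | 3.995 |

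**4. The wait after surgery.** Extra days before shipment are common to all of a patient's samples. Take L = 1%, D = 28 and an assumed 60 further days under the same conditions. Recovery is 0.99^88 = 0.41 for the first sample and 0.99^61 = 0.54 for the last. The ratio is still 0.99^-27 = 1.31, but both levels are far below the truth. Under first-order loss, this wait lowers absolute exposure and leaves the within-patient ratio unchanged.

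**5. If loss levels off.** As an illustration, let loss approach 30% at a rate of 0.1 per day, so that recovery is 1 - 0.3(1 - e^(-0.1s)). For D = 28, the ratio at hand-over is 0.971/0.718 = 1.35. After 30 more days it is about 1.02. A false trend therefore needs loss that is still progressing over the storage times in question.

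**The case against.** The strongest objection is that no loss has been shown. The rates above are assumptions, the largest ratios need both rapid loss and the longest course, and stable analytes would give no bias at all. This stands, and it is why the effect is stated as a range that starts at 1.00. Absence of stability data from the protocol does not mean that none exist. Section 1.4 describes a PK run-in and a companion PK study at the same dose, and the assay laboratory may hold suitable results.

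A reader might infer from Section 1.5 that one ATB compound turns into another in the stored tubes, since "Trifolirhizin is also expected to be highly active because it is rapidly biotransformed to maackiain". The documents do not support this. The conversion is stated for the living body, not for frozen saliva, and no section lists the saliva analytes. A product formed in storage would also be highest in the oldest samples and would show a fall, not a rise.

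A reader might also infer that the time course cannot be recovered by any means. That goes too far. The exact aliasing concerns linear trends within a patient. Course lengths differ, so patients on the same study day have different storage ages. This gives some between-patient information if course length is unrelated to concentration. Samples taken at different doses on the same day have almost equal storage age, so comparisons within a day are little affected.

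Finally, no last-day to first-day saliva comparison is planned, and storage age can already be calculated from the recorded times. Both are true. But the planned model is time-dependent, absolute levels matter for the bioavailability aim, and knowing the storage age does not break the aliasing without outside information on loss.

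**Conclusion.** The concern holds as a conditional one. The handling in Section 3.1 makes storage age and day on ATB perfectly inversely related within each patient, under warmer conditions than those required for tissue in the ATB accumulation studies. The documents contain nothing that rules storage loss out.

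The size is unknown. It is nil if the analytes are stable. At an assumed 1% per day with first-order loss and a flat true profile, the apparent rise is 6% over a 7-day course and 31% over a 28-day course, and it is larger if loss is faster. A long wait before shipment would lower absolute levels but would not enlarge the within-patient ratio under the same model. Formation in storage would reverse the direction.

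It would be wrong to conclude that ATB compounds do degrade in these tubes, or that a rise in saliva levels would be spurious; the documents show neither. Only the secondary saliva PK endpoint is affected. This is a low-cost improvement and does not threaten the trial's main result.

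**What to change.** 1. In Section 3.1, remove the 0 °C upper limit so that samples must be kept frozen at home, with a target of about -20 °C.
2. Transfer saliva to -80 °C at hand-over and hold it there until dry-ice shipment, as for tissue. Include samples already held; this limits further loss but does not restore what may have gone.
3. Derive the storage age of every sample from its recorded collection time and the surgery and shipment dates.
4. Report the saliva PK results with a sensitivity analysis for storage loss, running from zero loss to the largest loss compatible with the stability data.
5. Take those stability data from the assay laboratory if they exist. If not, run a small spiked-saliva check covering storage of 1 to 28 days under home-freezer conditions and one trip on freeze packs.
6. Analyse trifolirhizin and maackiain as a molar sum only if both are assayed in saliva.

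The cost is a wording change, freezer space of a kind already used for tissue, one derived variable and possibly one bench run. No patient procedure is added. The drawback is that some patients were treated before the current amendment (Section 7.2), so samples from before and after the change will have been handled differently within a group of about 14. Flag the handling regime in the dataset and in the analysis.
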